**Source of Information Used for Calculation**

The sources of information used for the calculations of CDAI and PRO2 subscores and total PRO2 score as described above are given in [Table 13-6](#) (the calculated scores from ERT data will not be used for data analysis). Hematocrit results collected from local laboratories and body weight measured at home due to COVID-19 impact will be used in CDAI calculation.

**Table 13-6. Sources of Information for Calculating CDAI and PRO2 Scores**

Variable in Calculation	Data Source
Ileocolonoscopy Procedure Date	ILEODAT in ILEO dataset from eCRF data for Screening, Week 10 and Week 58; QSTEST = “Date of Colonoscopy” in CDAI dataset from vendor ERT data for the rest of the visits
Visit Date	VISITDAT in VISDT dataset from eCRF data
Subject Activation Date on Electronic Device	QSORRES in CDAI dataset with QSTEST=“Date of Visit” and Visit=“Screening” from vendor ERT data
Stool Frequency Diary Data	QSSTRESN in DIARY dataset with QSTESTCD=“SOFSTOOL” from vendor ERT data
Abdominal Pain Diary Data	QSSTRESN in DIARY dataset with QSTESTCD=“ABDPAIN” from vendor ERT data
Subject Standard Weight	SEX_STD in DM dataset and HEIGHT_STD in VSPERF dataset from eCRF data will be used to determine the standard weight based on Appendix 4 .
Subject Actual Weight	WEIGHT_STD in VSPERF dataset from eCRF data
Hematocrit Value	CNVRESN in COVLAB dataset with LBTEST=“Hematocrit” from vendor Covance data or LBORRES in LB_HEM dataset with LBTEST=“Hematocrit” from eCRF data if collected in local laboratory due to COVID-19 impact

Note: eCRF = electronic case report form(s). ERT is the vendor that electronically collects patient and investigator reported outcomes.

**Appendix 4. Calculation of Standard Body Weight**

The following table will be used to determine the standard body weight for each subject. Height from the eCRF will be used and is assumed to be measured without shoes.

Women			
Height in cm (in shoes)*	Standard Weight in kg	Height in cm (in shoes)*	Standard Weight in kg
127	41.2	163	60.2
128	41.7	164	60.7
129	42.3	165	61.3
130	42.8	166	61.9
131	43.3	167	62.4
132	43.8	168	62.9
133	44.4	169	63.4
134	44.9	170	63.9
135	45.4	171	64.5
136	45.9	172	65.0
137	46.4	173	65.5
138	47.0	174	66.0
139	47.5	175	66.6
140	48.0	176	67.2
141	48.6	177	67.7
142	49.1	178	68.3
143	49.6	179	68.8
144	50.2	180	69.3
145	50.7	181	69.8
146	51.2	182	70.3
147	51.8	183	70.8
148	52.3	184	71.3
149	52.8	185	71.8
150	53.1	186	72.3
151	54.1	187	72.8
152	54.5	188	73.3
153	55.0	189	73.8
154	55.4	190	74.3
155	55.9	191	74.9
156	56.4	192	75.4
157	57.0	193	76.0
158	57.5	194	76.5
159	58.1	195	77.0
160	58.6	196	77.6
161	59.1	197	78.1

---

162	59.6	198	78.6
-----	------	-----	------

---

\* add 2.0 cm if shoeless. Please round height to a whole number and select the appropriate standard weight (eg, height 157.4 cm will be rounded to 157 cm; 157.5 cm will be rounded to 158 cm.)

Men			
Height in cm (in shoes)*	Standard Weight in kg	Height in cm (in shoes)*	Standard Weight in kg
142	54.4	179	71.9
143	54.9	180	72.4
144	55.4	181	73.0
145	55.8	182	73.6
146	56.3	183	74.3
147	56.8	184	74.8
148	57.2	185	75.5
149	57.7	186	76.2
150	58.2	187	76.9
151	58.6	188	77.6
152	59.1	189	78.2
153	59.6	190	78.8
154	60.0	191	79.6
155	60.5	192	80.4
156	61.0	193	81.2
157	61.4	194	82.1
158	61.9	195	82.9
159	62.2	196	83.8
160	62.6	197	84.7
161	62.9	198	85.4
162	63.3	199	86.1
163	63.7	200	86.7
164	64.1	201	87.4
165	64.6	202	88.0
166	65.0	203	88.8
167	65.5	204	89.4
168	66.0	205	90.1
169	66.6	206	90.7
170	67.1	207	91.4
171	67.6	208	92.1
172	68.1	209	92.7
173	68.7	210	93.4
174	69.2	211	94.1
175	69.7	212	94.8

---

176	70.3	213	95.5
177	70.8	214	96.1
178	71.3		

---

\* add 2.0 cm if shoeless. Please round height to a whole number and select the appropriate standard weight (eg, height 157.4 cm will be rounded to 157 cm; 157.5 cm will be rounded to 158 cm.)

**Appendix 5. Simple Endoscopic Score for Crohn’s Disease (SES-CD)**

Variables	Score			
	0	1	2	3
Size of ulcers (cm)	None	Aphthous ulcers (diameter 0.1-0.5)	Large ulcers (diameter 0.5-2)	Very large ulcers (diameter > 2)
Ulcerated Surface (%)	None	< 10	10-30	> 30
Affected surface (%)	Unaffected segment	< 50	50-75	> 75
Presence of narrowings	None	Single, can be passed	Multiple, can be passed	Cannot be passed

Total SES-CD: sum of the values of the 4 variables for the 5 bowel segments. Values are given to each variable and for every examined bowel segment (eg, rectum, left colon, transverse colon, right colon, and ileum)  
 {Daperno 2004}

## Appendix 6. Study Treatment Failure Rules

Study treatment failure rules apply to treatment failure that occurs during the course of the study. Study treatment failure rules will be applied to all efficacy endpoints, unless otherwise specified. All efficacy data will be censored (set to missing) after treatment failure criteria are met, regardless of the observed data. Subjects who do not have sufficient measurements after censoring to determine the dichotomized endpoint(s) will be considered non-responder for corresponding endpoint(s). Study treatment failure rules override other data handling rules.

Subjects who have any of the following events will be considered a study treatment failure after the earliest event through the end of the Induction Study (if the event occurred during Induction) or through the end of the Maintenance Study (if the event occurred during Maintenance), regardless of the actual efficacy data collected. Induction baseline will be referenced when calculating the potentially effective use for Induction Studies, and Maintenance baseline will be referenced when calculating the potentially effective use for Maintenance Study.

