### **3.6. Disease Worsening Criteria**

Subjects meeting the following disease worsening criteria evaluated after Week 11 must be discontinued from blinded treatment and will be offered the option to receive open-label filgotinib by entering into the separate LTE study (GS-US-419-3896).

- Increase in CDAI score  $\geq$  100 points from the Week 10 value and CDAI score  $\geq$  220 points at 2 consecutive visits.
  - The disease worsening visits may include unscheduled visits (eg, a study visit followed by an unscheduled visit, or 2 sequential unscheduled visits anytime subsequent to the Week 11 visit).
- If a subject experiences significant worsening of underlying CD, which requires any of the prohibited medications (refer to Section 5.4.2), or surgical intervention at any point during the study, treatment discontinuation should be considered at investigator's discretion, in consultation with medical monitor if feasible (refer to Section 3.5.2); these subjects do not qualify for LTE study.

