**Table 6-4. Composite Estimand 1 (Primary Analysis) for Clinical Remission by CDAI**

Attributes	Composite Estimand 1
Treatment	Filgotinib 200 mg, filgotinib 100 mg, or placebo
Population	Full Analysis Set as defined in Section 3.1.2
Component-level endpoint	CDAI subscore for each component at Week 10 for Induction Studies and at Week 58 for Maintenance Study
Subject-level endpoint	CDAI clinical remission status (Yes/No) at Week 10 for Induction Studies and at Week 58 for Maintenance Study If CDAI < 150, then the subject will be defined as achieving clinical remission at Week 10 or at Week 58, respectively. If the above remission criterion is not met

	or the CDAI is missing, the subject will be considered as not achieving clinical remission by CDAI.
Handling of missing data (component-level endpoint)	If the subscore for 1 or 2 components are missing at Week 10 (or Week 58), then the subscore will be imputed using LOCF imputation method (see Section 6.1.1). If the subscores for 3 or more components are missing, then missing subscores will not be imputed, and the CDAI will be considered missing.
Handling of missing data due to intercurrent events (subject-level endpoint)	Subjects who meet treatment failure criteria (ie, take potentially effective medications other than study treatment as defined in Appendix 6) or prematurely discontinue from the study without available assessment result are considered as not achieving clinical remission by CDAI
Population-level summary	Difference in proportions in clinical remission by CDAI, comparing a filgotinib dose group to placebo group

CDAI = Crohn’s Disease Activity Index; LOCF = last observation carried forward

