### 1) Potentially effective corticosteroid use

Potentially effective corticosteroids, for the purpose of this SAP, are corticosteroids that may impact the disease under study. **Potentially effective corticosteroids** include the following corticosteroids when administered for the indication of CD:

a) Commencement of:

Any steroid administered intramuscularly (IM), intravenously (IV), orally (PO), or rectally (PR) at any dose for 7 or more continuous days

- This rule applies regardless if a change in drug, dose, or route (from IM to IV to PO or PR or vice versa) occurs within the seven continuous days; and it includes oral steroids with intended local actions (eg, budesonide)

b) Escalation of concomitant steroid dose above the baseline dose for 7 or more continuous days. The baseline steroid dose is defined as the dose at Day 1 of induction if the escalation occurs in the Induction Study, or Day 1 of maintenance (maintenance baseline) if the escalation occurs in the Maintenance Study. Prednisone equivalent dose will be used to determine escalation of concomitant systemic steroid dose even if there is a change in drug or route. For steroids with predominant local effect (eg, budesonide or any rectally administered steroid), the dose escalation rule will apply to scenarios where the post-baseline dose is above the baseline dose via the same drug and the same route for 7 or more continuous days.

Potentially effective steroid use only includes use of steroids administered via routes that are IM, PO, IV, or PR. The below steroids will **not** be considered potentially effective steroids regardless of indication for use:

- A) ocular steroids (ie, eye drops)
- B) topical steroids (eg, cutaneously applied solely to the skin, or topically applied to the nasal mucosa)
- C) inhaled steroids (eg, inhalational fluticasone for asthma)
- D) intra-articular steroids (steroids administered directly into a joint)
- E) neuraxial steroids (steroids administered into the epidural or spinal space)

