## **2) Potentially effective immunomodulator use**

### **Commencement of a different class of oral, IM, SC, or IV immunomodulator drugs**

(where the subject was not previously taking concomitant immunomodulators of the same class on Day 1 of induction or maintenance), including but not limited to 6-MP, azathioprine, MTX, 6-thioguanine, and prohibited immunomodulators including but not limited to cyclosporine, leflunomide, tacrolimus, thalidomide regardless of dose, for 7 continuous days. The use of an immunomodulator will be considered potentially effective when it is administered for the indication of CD.

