## **3) Potentially effective biologic agent use**

**Commencement of a biologic agent** including but not limited to TNF- $\alpha$  antagonists, IL-12/23 antagonists, and vedolizumab (or similar agents), regardless of indication for use and duration.

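### Surgery for Crohn's disease is not a study treatment failure event, so an operated subject who stays in the study can count as in clinical remission

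*SAP*

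**What the plan says.** SAP Appendix 6 sets the failure rule for all efficacy endpoints: "Subjects who have any of the following events will be considered a study treatment failure after the earliest event". Efficacy data after the event are set to missing, whatever was observed, through the end of the Induction or Maintenance Study in which it occurred. Three events follow:

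- "Potentially effective corticosteroid use": for Crohn's disease, for 7 or more continuous days.
- "Potentially effective immunomodulator use": a different class, for Crohn's disease, for 7 continuous days.
- "Commencement of a biologic agent": for any indication or duration.

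The estimand tables follow the same line. Table 6-4 (CDAI) explains the failure criteria as subjects who "take potentially effective medications other than study treatment as defined in Appendix 6". Tables 6-2, 6-3 and 6-5 use the same wording, and Tables 6-6 and 6-7 nearly the same. The other intercurrent-event route to non-remission is for subjects who "prematurely discontinue from the study without available assessment result are considered as not achieving clinical remission by CDAI". The reasons list for dichotomous endpoints in SAP 6.1 has an entry for rescue medication and none for surgery.

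Protocol Section 3.6 deals with significant worsening that requires prohibited medication "or surgical intervention at any point during the study, treatment discontinuation should be considered at" the investigator's discretion. Section 3.5.1 names elective or emergency surgery as a reason to consider interrupting study drug, allows visits to continue meanwhile, and foresees resumption.

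**The concern.** The primary estimands are composite: a subject who needs another potentially effective drug counts as a failure even if the score at the visit is good. Surgery for Crohn's disease raises the same question, because a good score afterwards may reflect the operation and not the study drug. Protocol Section 3.6 itself puts prohibited medication and surgery side by side as marks of significant worsening, but the SAP acts only on medication.

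An operation can change CDAI directly. In SAP Table 13-1, anal fissure, fistula or abscess carries 20 points, other fistula 20, and a definite abdominal mass 5 × 10 = 50. These sum to 90 points, against a remission threshold of 150.

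At stake are clinical remission by CDAI (non-EU co-primary), clinical remission by PRO2 (EU co-primary), and the key secondary endpoints built on them. In Induction, PRO2 remission after surgery also satisfies the entry criterion for Maintenance and its Full Analysis Set.

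**Working it through.** **Step 1. Follow an operated subject who stays, starts no listed drug and is assessed at Week 10 or Week 58.**

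- *Appendix 6:* no event applies. Perioperative steroids trigger the rule only if given for Crohn's disease for at least 7 continuous days.
- *Discontinuation without an assessment:* does not apply, because an assessment exists.
- *Disease worsening (Protocol 3.6):* defined by CDAI at two consecutive visits, not by surgery.
- *Drug discontinuation for disease worsening (SAP 6.1):* a reporting category for subjects who miss the endpoint, not a classification rule.
- *Missing segment scored 12 (SAP 6.1.2):* affects endoscopic response and endpoints containing it, such as the EU key secondary combining PRO2 remission with endoscopic response. It applies only if the segment is missing; a procedure that leaves every segment scorable is untouched.
- *Sensitivity analyses (SAP 6.2.5):* estimand 2 keeps the medication-only definition. Multiple imputation and the tipping-point analysis act on missing data, so observed post-operative scores pass through.

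A CDAI below 150, or PRO2 within its limits, is therefore counted as clinical remission.

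**Step 2. Weight of one subject.** Maintenance plans 60 placebo and 120 filgotinib subjects (Protocol 8.9.2).

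- Placebo: 1/60 = 1.7 points. Filgotinib: 1/120 = 0.8 points.
- Assumed 1-4% operated: 0.01 × 60 = 0.6 to 0.04 × 60 = 2.4 placebo; 0.01 × 120 = 1.2 to 0.04 × 120 = 4.8 filgotinib, per dose comparison.

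These are upper bounds. Classification changes only for those who stay, avoid the listed drugs, are assessed and meet the remission criterion.

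**Step 3. The plan's power figure.** The plan states 94% overall for 50% against 20% on both co-primaries at 2-sided 0.05, as the product of two powers. The pooled-variance normal approximation gives:

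- Pooled rate (60 × 0.20 + 120 × 0.50)/180 = 0.40.
- Null SE = √(0.40 × 0.60 × (1/60 + 1/120)) = 0.0775. Alternative SE = √(0.20 × 0.80/60 + 0.50 × 0.50/120) = 0.0689.
- Power = Φ((0.30 − 1.96 × 0.0775)/0.0689) = 0.984; squared, 96.9%.
- With a continuity correction, 0.9755² = 95.2%, close to the stated 94%.

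**Step 4. Scenarios.** Take 20% and 50% as the Week 58 clinical remission rates with surgery counted as failure, then add operated subjects scored as remitters. Endoscopic power stays at 0.984; no continuity correction.

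| Added, placebo / filgotinib (points) | Difference (points) | Overall power |
|---|---|---|
| 0 / 0 | 30 | 96.9% |
| 2 / 2 | 30 | 96.6% |
| 2 / 1 | 29 | 95.9% |
| 2 / 0 | 28 | 95.0% |
| 0 / 2 | 32 | 97.7% |
| 5 / 0 | 25 | 89.7% |
| 0 / 5 | 35 | 98.2% |

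The two 5-point rows exceed the assumed 4% ceiling for all operated subjects and only mark an extreme. In Induction one subject in 220 is 0.45 points, so the effect is smaller.

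**The case against.** The strongest reply is that the plan is consistent. Appendix 6, the estimand tables and the reasons list are all medication-based, and using observed data after surgery is a recognised strategy. It stands that there is no internal contradiction. But the plan never says that it chose that strategy for surgery, and the result sits badly with a composite approach that fails a subject for starting a biologic for any reason.

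It also stands that few subjects should be affected. Entry excludes symptomatic strictures, non-perianal fistulae and likely need for surgery. Maintenance takes only Week 10 PRO2 remitters or endoscopic responders. Both co-primaries must succeed, so endoscopy partly guards the dose-level claim. These features lower frequency and impact but do not classify the operated subject.

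Four stronger readings are tempting and unsupported:

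- *Surgery is scored as success.* Observed remission is; an operated subject who misses the thresholds is still a non-remitter.
- *The gap favours filgotinib, or occurs mainly on placebo.* The documents give no surgery rate by arm. More operated remitters on placebo would work against filgotinib; more on filgotinib would inflate the difference.
- *The sample size or power is wrong.* No stated figure depends on this rule.
- *Surgery dates are already on the eCRF.* The documents do not say so. Protocol 7.1.1 excludes surgery itself from adverse events, though the underlying condition may be reportable, and the surgery item in SAP 5.2 is history before treatment.

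**Conclusion.** The point holds. As written, a subject operated on for Crohn's disease who stays and is assessed can be counted as in clinical remission by CDAI or PRO2, and no other rule or planned sensitivity analysis catches this. The likely effect is small: under the assumed 1-4%, at most about two placebo and five filgotinib subjects per dose, at 1.7 and 0.8 points each. In the 2-point scenarios the Maintenance difference lies between 28 and 32 points, with overall power of 95.0% to 97.7% against 96.9% with no such subjects. All of this rests on assumed rates, and the sign is unknown. That is a reason to settle the rule while blinded, because a few disputed remitters in an arm of 60 are hard to argue about afterwards. It should be changed, but it does not undermine the design.

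**What to change.** Add a fourth event to SAP Appendix 6: surgery for Crohn's disease after the first dose of the relevant study, with failure from the date of surgery to the end of that Induction or Maintenance Study, for all efficacy endpoints. Before unblinding, list which procedures count, for example whether minor perianal procedures are excluded, since perianal fistulae are allowed at entry. Align Tables 6-2 to 6-7, and add surgery to the reasons list in SAP 6.1. Confirm the data source for the type and date of surgery.

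This changes the analysis classification only; the protocol's handling of operated subjects is untouched. The cost is SAP wording, a few subjects reclassified, and possibly some manual identification of surgeries if no dedicated field exists. The SAP is to be approved before database finalization, so the change fits its own timetable.

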### 1) Potentially effective corticosteroid use

Potentially effective corticosteroids, for the purpose of this SAP, are corticosteroids that may impact the disease under study. **Potentially effective corticosteroids** include the following corticosteroids when administered for the indication of CD:

a) Commencement of:

Any steroid administered intramuscularly (IM), intravenously (IV), orally (PO), or rectally (PR) at any dose for 7 or more continuous days

- This rule applies regardless if a change in drug, dose, or route (from IM to IV to PO or PR or vice versa) occurs within the seven continuous days; and it includes oral steroids with intended local actions (eg, budesonide)

b) Escalation of concomitant steroid dose above the baseline dose for 7 or more continuous days. The baseline steroid dose is defined as the dose at Day 1 of induction if the escalation occurs in the Induction Study, or Day 1 of maintenance (maintenance baseline) if the escalation occurs in the Maintenance Study. Prednisone equivalent dose will be used to determine escalation of concomitant systemic steroid dose even if there is a change in drug or route. For steroids with predominant local effect (eg, budesonide or any rectally administered steroid), the dose escalation rule will apply to scenarios where the post-baseline dose is above the baseline dose via the same drug and the same route for 7 or more continuous days.

Potentially effective steroid use only includes use of steroids administered via routes that are IM, PO, IV, or PR. The below steroids will **not** be considered potentially effective steroids regardless of indication for use:

- A) ocular steroids (ie, eye drops)
- B) topical steroids (eg, cutaneously applied solely to the skin, or topically applied to the nasal mucosa)
- C) inhaled steroids (eg, inhalational fluticasone for asthma)
- D) intra-articular steroids (steroids administered directly into a joint)
- E) neuraxial steroids (steroids administered into the epidural or spinal space)

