### **5.4.3. Corticosteroid Tapering**

Starting at Week 14, subjects who are on concomitant steroids must begin tapering steroid therapy. The dose should be reduced at a rate starting at 2.5 mg per week up to 5 mg per week (or equivalent taper if not prednisone) until subject is no longer on steroids. Subjects who are on budesonide should have their daily dose reduced by 3 mg every 3 weeks until they are completely off steroids. For subjects undergoing taper, steroids may be increased or restarted at doses up to and including their baseline dose if return of symptoms is apparent. These subjects will not be considered treatment failures. Subjects who need to restart or increase steroid treatment at a dose that exceeds their baseline dose of steroids (dose may not exceed 30 mg prednisone [or equivalent] or budesonide 9 mg/day) will be considered treatment failures for all clinical end points but will be permitted to remain in the study.

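### Maintenance Study: as written, SAP Appendix 6 rule 1(a) fails a baseline steroid user who tapers to zero and restarts at or below the baseline dose, which Protocol 5.4.3 says is not a failure during the taper

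*SAP*

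**What the plan says.** **Protocol, Section 5.4.3 (repeated in the synopsis).** Subjects on steroids must begin tapering at Week 14. The section then allows: "For subjects undergoing taper, steroids may be increased or restarted at doses up to and including their baseline dose if return of symptoms is apparent". It adds: "These subjects will not be considered treatment failures". Only a restart or increase above the baseline dose is a failure, and that is for clinical endpoints.

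**SAP, Appendix 6, rule 1.** The rule covers steroids given for Crohn's disease and has two limbs.
- Limb (a) is commencement of "Any steroid administered intramuscularly (IM), intravenously (IV), orally (PO), or rectally (PR) at any dose for 7 or more continuous days".
- Limb (b) is "Escalation of concomitant steroid dose above the baseline dose for 7 or more continuous days". Systemic steroids are compared by prednisone-equivalent dose. Budesonide and rectal steroids are compared only within the same drug and route.

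**SAP, Appendix 6, opening text.** The rules apply to all efficacy endpoints unless stated otherwise. On consequence: "All efficacy data will be censored (set to missing) after treatment failure criteria are met, regardless of the observed data". On precedence: "Study treatment failure rules override other data handling rules". On the reference point: "Maintenance baseline will be referenced when calculating the potentially effective use for Maintenance Study".

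**SAP, Appendix 6, rule 2 (immunomodulators).** This rule does carry a prior-use limit: "where the subject was not previously taking concomitant immunomodulators of the same class on Day 1 of induction or maintenance". Rule 1(a) has none.

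**The concern.** A subject on steroids at maintenance baseline who tapers to zero, flares, and restarts at or below the baseline dose for 7 or more days meets the words of rule 1(a). The protocol tells the investigator that the same action, in a subject undergoing taper, is not a failure.

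Under the SAP, all later efficacy data for that subject are set to missing. The subject then counts as a non-responder at Week 58 for clinical remission (CDAI or PRO2) and for endoscopic response, whatever was observed. Because the failure rules take precedence, no other SAP rule restores the protocol's classification.

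The primary estimands (SAP Tables 6-2, 6-4 and 6-6) import Appendix 6 directly. The second estimands and the multiple-imputation analyses keep the same failures, so they would not reveal the difference. Two programmers could code 1(a) differently and each defend the choice from the text.

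**Working it through.** **1. The rules side by side.** Take, for illustration, a subject on prednisone 10 mg for Crohn's disease at maintenance baseline.

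| Event during taper | Protocol 5.4.3 | 1(a) as written | 1(b) |
|---|---|---|---|
| Down to 5 mg, back to 10 mg | not a failure | not a commencement | not above baseline |
| Down to 0, restart 5 mg for 5 days | not a failure | under 7 days | not above baseline |
| Down to 0, restart 5 mg for 14 days | not a failure | **failure** | not above baseline |
| Down to 0, restart 15 mg for 14 days | failure (clinical endpoints) | failure | failure |

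The conflict is confined to the third row: a full stop, then a restart at or below the baseline dose for 7 or more days. The protocol's permission must reach at least some such cases, because only a drug that has been stopped can be restarted.

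**2. Different baselines do not explain it.** The steroid dose must stay stable to Week 14 (Protocol 4.2.1 criterion 9c and 4.5.1 criterion 3), and Maintenance starts at Week 11. The induction and maintenance baseline doses should therefore match.

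**3. When subjects can reach zero.** Protocol 5.4.3 gives 2.5 to 5 mg per week for prednisone, and 3 mg every 3 weeks for budesonide, from Week 14.
- Prednisone 30 mg: 30/5 = 6 to 30/2.5 = 12 weeks, so Week 20 to 26.
- Prednisone 10 mg: 10/5 = 2 to 10/2.5 = 4 weeks, so Week 16 to 18.
- Budesonide 9 mg: (9/3) × 3 = 9 weeks, so Week 23.

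All of these fall between Week 10 and Week 58. The Week 10 analyses cannot be touched by the taper.

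**4. A clash inside the SAP.** Table 6-1 fails the corticosteroid-free endpoint for re-initiation within 6 months before Week 58, which is from about Week 58 − 26 = 32. The 10 mg user could be off by Week 18, restart from Week 20 to 22, and then be steroid-free for 58 − 22 = 36 weeks. The re-initiation sentence in Table 6-1 does not fail this subject. Rule 1(a) as written does, and it takes precedence.

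**5. Leverage.** The plan's figure of 176 eligible subjects per dose reproduces: 2 × 220 × 0.40 = 176. Allocated 2:1 this is 117.3 and 58.7, about 117 and 59. One reclassified subject moves the rate by 100/117 = 0.85 points on filgotinib or 100/59 = 1.69 points on placebo.

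**6. Distance to losing significance.** The planned 50% versus 20% is close to 59/117 versus 12/59. Single-stratum CMH p-values, without continuity correction:

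| Filgotinib | Placebo | p |
|---|---|---|
| 59/117 | 12/59 | 0.0001 |
| 59/117 | 20/59 | 0.038 |
| 59/117 | 21/59 | 0.063 |
| 41/117 | 12/59 | 0.045 |
| 40/117 | 12/59 | 0.058 |

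The two directions start from different places. If the planned rates are taken as counted under 1(a) as written, moving to the protocol classification can only add responders, and it takes 21 − 12 = 9 more on placebo with none added on filgotinib. If they are taken as counted under the protocol, applying 1(a) can only remove responders, and it takes 59 − 40 = 19 fewer on filgotinib with none removed on placebo.

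**7. Direction.** The documents give no share on baseline steroids and no restart rate, so the following inputs are assumptions. Suppose 50% are on steroids and 30% of restarters would otherwise respond.
- If 30% of filgotinib and 10% of placebo users restart, the rates become 50 − 100(0.5 × 0.3 × 0.3) = 45.5 and 20 − 100(0.5 × 0.1 × 0.3) = 18.5, a difference of 27.0 points.
- If 20% and 40% restart, they become 47.0 and 14.0, a difference of 33.0 points.

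Either sign is possible.

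**The case against.** **The narrower reading is the natural one.** Appendix 6 ties potentially effective use to maintenance baseline. On that footing, commencement means starting something not in use at baseline, and limb (b) judges baseline users by dose. The literal reading also gives an odd result: going from 2.5 mg back up to baseline passes, while restarting 2.5 mg after reaching zero fails. And it would make the Table 6-1 re-initiation sentence largely redundant. All of this stands as evidence of likely intent. It does not put the limit into the rule, and rule 2 shows that the authors wrote such a limit where they wanted one.

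**The protocol protects only subjects undergoing taper.** This stands. The scheduled taper ends by about Week 26, and neither document says whether a later restart is still covered. A reader might infer that every restart up to Week 58 is in conflict; the documents do not support that.

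**The effect would be visible.** SAP 6.1 tabulates, by treatment, subjects who miss an endpoint because data were censored for rescue medication. That gives an upper bound per arm, but it pools all kinds of rescue and does not separate permitted restarts.

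**A stricter rule may have been intended and disclosed.** SAP 6.6, on changes from the protocol, is largely redacted, so this cannot be excluded. Disclosure there would still leave the wording of 1(a) open to two codings.

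**Conclusion.** The point holds in a narrow form. In the Maintenance Study, rule 1(a) as written fails a subject who was on steroids for Crohn's disease at maintenance baseline, tapered to zero, and restarted at or below the baseline dose for 7 or more days. Protocol 5.4.3 does not count such a subject as a failure while the taper is under way. Both co-primary endpoints at Week 58 are affected. A consistent reading exists but is not written down.

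Three stronger readings are tempting and not supported.
- **The rule biases the comparison towards filgotinib.** The direction depends on restart rates that the documents do not give, and either sign is possible.
- **The Maintenance conclusion is in doubt.** At the planned effect it would take 9 extra placebo responders or 19 fewer filgotinib responders, with the other arm unchanged. This was checked for 200 mg at 0.05, ignoring strata. What is at stake is correct classification and the point estimate.
- **The SAP's 7-day minimum for above-baseline use and its extension of failure to endoscopic response are errors of the same kind.** They are defensible choices and may be recorded in the redacted part of SAP 6.6.

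This should be fixed, at modest severity.

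**What to change.** Before unblinding, add one sentence to rule 1(a), along these lines:

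> In the Maintenance Study, resumption after taper of a corticosteroid the subject was taking for CD at maintenance baseline (systemic steroids compared by prednisone-equivalent dose; budesonide or rectal steroids by same drug and same route) is not a commencement and is judged only under 1(b); starting any other steroid remains a commencement under 1(a).

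Also state how long after the last taper step this applies, since the protocol does not say.

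A simpler limit, confining 1(a) to subjects not on steroids at baseline, should not be used. It would exempt every baseline user. Limb (b) compares budesonide and rectal steroids only within the same drug and route, so a prednisone user who adds budesonide, or a budesonide user who adds a rectal steroid, could escape both limbs and genuine rescue would count as response.

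The cost is one sentence, one stated time limit, and the matching programming check. No extra sensitivity analysis is needed once the wording is settled.
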